#### Motor Evoked Potentials (MEPs)

Subjects will be seated in a comfortable chair for all procedures. Single-pulse TMS will be used to evoke MEPs from the right first dorsal interosseous (FDI) muscle.

Electromyographic recordings will be made from the right FDI using two Ag–AgCl surface electrodes arranged in a belly-tendon montage. Signals will be sampled at a rate of 5 kHz, amplified #1000 and filtered 20–1000 Hz before we store on a computer for offline analysis. Single-pulse TMS with monophasic waveform will be applied using a Magventure Magpro X100 magnetic stimulator Magventure, Farum, Denmark connected to a figure-of-eight magnetic coil external wing diameter, 90 mm. The coil will be held tangentially to the skull over the left M1, with the handle pointing 45° posterolaterally. The optimal scalp site for evoking MEPs in the right FDI will be identified and marked using a watersoluble felt marker, and the intensity of stimulation will be adjusted to evoke baseline MEPs of approximately 1 mV amplitude measured peak-to peak.

#### TBS Paradigms

iTBS and cTBS will be applied with biphasic waveform using a Magventure Magpro Magventure, Farum, Denmark. One of two cTBS and two iTBS paradigms with varying pulse configurations will be employed in this study. cTBS50 consists of a total of 600 stimuli applied in bursts of 3 stimuli at 20 ms intervals 50 Hz, with bursts repeated at 200ms intervals 5Hz. In the cTBS30 paradigm, bursts consisted of 3 stimuli applied at intervals of 33.3 ms 30 Hz, with bursts repeated at 167 ms intervals 6 Hz.

As with the cTBS50 paradigm, cTBS30 consists of a total of 600 stimuli. iTBS50, consists of a total of 600 stimuli applied in bursts of 3 stimuli at 20 ms intervals 50 Hz, with bursts repeated at 200ms intervals 5Hz and an 8 second intertrain interval between triplets. iTBS30 consists of bursts consisted of 3 stimuli applied at intervals of 33.3 ms 30 Hz, with bursts repeated at 167 ms intervals 6 Hz for three bursts then an 8 second intertrain interval.

In Experiment 1, the optimal burst frequency for both cTBS and iTBS will be determined and that optimal cTBS and iTBS frequency will be utilized in this portion of the study. Subjects will view movie clips tailored to induce primary affective states during the iTBS or cTBS protocol targeted to either dlPFC or area M1.

### TMS-EEG

TMS-EEG recordings may be collected at various points throughout the study. During TMS-EEG recordings, subjects will be instructed to listen to white noise.

### BIOMARKERS

Cortisol and other biomarkers may be collected at points during the study.

### OTHER TASKS/QUESTIONNAIRES:

Participants will be asked to perform the critical feedback task CFT at various points in the study. This is a simple computer-based question and answer task that asks the participant to perform mental math and provides them with accurate or bogus feedback on their performance.

- Hamilton rating scale for depression (HAMD)
- Montgomery–Asberg Depression Rating Scale
- Beck depression inventory
- Inventory of depressive symptoms
- Other mood questionnaires
- Emotion Induction task
- Emotional identification task

### Video Recording

-Video recordings will be conducted during clinical assessments and interviews for participants who consent to video recordings. More details are indicated in section 2d.

---

#### **b. Procedure Risks**

These methods are the least risky because the intervals of treatment have been shown to be appropriate for theta burst stimulation in the motor system with no adverse outcomes.

---

#### **c. Use of Deception in the Study**

No deception will be used.

---

#### **d. Use of Audio and Video Recordings**

We will offer study participants the option of videotaping the clinical assessments conducted with them while enrolled in the study. They will have to sign a separate consent for this to occur. The video recordings will be recorded using Zoom video from an encrypted Stanford owned laptop. The recordings will be available for training purposes for study personnel only. We will not use or distribute the videos to outside personnel or scientific meetings etc. unless directly indicated by the participant on the video consent form attached in section 13.

---

#### **e. Alternative Procedures or Courses of Treatment**

N/A

---

f. **Will it be possible to continue the more (most) appropriate therapy for the participant(s) after the conclusion of the study?**

N/A

---

g. **Study Endpoint(s)**

Because this is a mechanistic study and not a clinical trial, the primary endpoint is an assessment of the duration of effect of an application of TBS. We will assess the findings of the trial after all subjects have been run. We will not be performing interim analysis as this is not a treatment study and the risks of the TMS intervention are either minor or very rare.

---

### 3. BACKGROUND

---

a. **Past Experimental and/or Clinical Findings**

Theta-Burst Stimulation

There is early indication that utilizing TBS, which mimics natural brain rhythms, is an effective stimulation method for modulation of human cortex Huang, Edwards, Rounis, Bhatia, & Rothwell, 2005. While first utilized in the motor cortex, TBS has been since utilized in the limbic and cognitive areas with some early success in treating depression Chung, Hoy, & Fitzgerald, 2015. The benefits of this form of stimulation is that it appears to allow for a reduction in the time of treatment while maintaining a similar efficacy to traditional 40 min 10Hz rTMS stimulation in an early comparison study Bakker et al., 2015. Stimulation of the primary motor cortex M1 specifically, can influence both motor output and pain perception in both healthy and chronic pain populations Zaghi et al., 2010; Sacco et al., 2014. Associated changes in brain activity can be detected using functional magnetic resonance imaging MRI methods. There is emerging evidence from the motor system that the spacing or timing between theta burst trains is important in long-term potentiation/depression LTP/LTD. If the train goes on for two long without a necessary time interval, there is a reversal of the initial direction LTP or LTD Gamboa, Antal, Moladze, & Paulus, 2010.

TBS Burst frequency

Originally, the TBS burst frequency was determined to be 50Hz at 5Hz intervals. Recently, a modified version of the inhibitory form of TBS continuous---cTBS was demonstrated to produce more consistent suppression of the motor evoked potential MEP than the traditional form of cTBS. This modified form has been used in treatment applications with success. For the excitatory form of TBS intermittent---iTBS, iTBS30 has demonstrated a similar change in the MEP as iTBS50. Modifications to the burst frequency have been described to potentially affect clinical outcome in TBS for MDD. While single experiments have been performed demonstrating differences between TBS30 and TBS50, there has yet to be a study comparing iTBS and cTBS in the same participants between these two burst frequency conditions.

Spaced Theta-Burst Stimulation

Spaced theta-burst stimulation (sTBS) is a patterned application of TBS that was studied initially in animal models. It has been demonstrated that en masse stimulation with TBS

produces effects that are opposite to the intended effect. Spaced, patterned theta-burst is therefore required. sTBS was assessed in healthy controls with MEP change and it has been demonstrated that RMT70 produces 2 hours of suppression of the MEP which is affected by preceding hand activation. This approach has been assessed for saccade induction with non-linear increases in saccades. Recently, the technique has been applied to disease conditions such as hemispatial neglect and depression.

#### Intersession Interval of Spaced TBS

The optimal ISI is unknown for iTBS and cTBS. It appears that 15 minutes as has previously used by one group for depression, may be too short for late stage LTP induction in the case of iTBS. For cTBS, 10-15 min has been most regularly used, but longer ISI have yet to be explored.

#### TBS-induced Change to Resting State Functional Connectivity

It has been demonstrated that rTMS and more specifically TBS are functional connectivity (fc) modulators that are stimulation parameter specific (excitatory or inhibitory). Furthermore, it has been demonstrated that patterned TBS application produces changes in fc MRI that are correlated with changes in MEP. It has been demonstrated that optimized ISI can produce an optimized change in the fc. Furthermore, it has been demonstrated that relative amounts of fc within the targeted neural network is correlated with change or no change in the fc and change or no change in the MEP. This property has been reflected in treatment application as well.

#### TBS-induced Change to IL TMS-fMRI

IL TMS-BOLD has been demonstrated to reflect inherent network properties of the TMS targeted neural network. It has been demonstrated that pharmacology or TBS can change these properties as reflected by the differential BOLD activation. One group has demonstrated that TBS to a targeted neural network can change the BOLD activation after IL TMS-BOLD as compared to pre TBS IL TMS-BOLD.

---

#### b. Findings from Past Animal Experiments

None

---

### 4. DEVICES USED IN THE STUDY

---

#### a. Investigational Devices (Including Commercial Devices Used Off-Label)

Investigational Device 1	
Name:	MagPro X100
Description:	Transcranial Magnetic Stimulation Device with theta burst stimulation
Significant Risk? (Y/N)	N
Rationale for Non-Significant Risk	The 'traditional 10Hz TMS' is on label and the theta burst stimulation is off label. It is the same device for both. The Magventure is about to be approved by the FDA for depression in 2 weeks. When that happens, the 'traditional 10Hz' stimulation will be on label with an approved device. The theta burst stimulation is minimal risk because the risk of seizure is very low (only reported once in literature) and there is no other risk other than minimal scalp irritation. We will be using an approved device 'off label' stimulation parameters which has a lower risk profile than the on label approved parameters.
Investigational Device 2	

Investigational Device 1	
Name:	MRI-safe infrared diode laser stimulator
Description:	MRI-safe infrared diode laser stimulator
Significant Risk? (Y/N)	N
Rationale for Non-Significant Risk	Does not fulfill the definition of a significant risk device.
Investigational Device 3	
Name:	NextStim
Description:	NextStim TMS device
Significant Risk? (Y/N)	N
Rationale for Non-Significant Risk	NextStim is an FDA-approved TMS device for treatment of depression

---

## 5. PARTICIPANT POPULATION

---

### a. Planned Enrollment

we will recruit 60 healthy participants only at Stanford-affiliated sites

### b. Age, Gender, and Ethnic Background

Participants will be 18-80 year-old right handed male and female subjects with no history of psychiatric or neurological diagnoses and no current use of psychoactive medications. They will be recruited to participate in this study, all of whom will be blinded to the purpose of the study. All subjects will be screened for any contraindications to TMS (23) and will give their informed written consent prior to participation. This study is approved by the Stanford University Institutional Review Board and performed in accordance with the Declaration of Helsinki

### c. Vulnerable Populations

We will not include children, pregnant women, decisionally impaired. We will include economically/educationally disadvantaged and homeless. We will also include employees and students rTMS is a low-risk procedure, but we will ensure all safety measures are taken for these participants.

### d. Rationale for Exclusion of Certain Populations

Women and minorities are included. Children are not because they are typically excluded from rTMS studies.

### e. Stanford Populations

Employees, students and lab personnel may sign up for this study in compliance HIPAA policy.

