**PARTICIPANTS**

We will recruit 60 healthy controls for this study 30 participants in MRI+rTMS/TBS group and 30 participants in MRI only group. Participants will be 18-80 year-old right handed male and female with no history of psychiatric or neurological diagnoses and no current use of psychoactive medications. They will be recruited to participate in this study, all of whom will be blinded to the purpose of the study. All subjects will be screened for any contraindications to TMS and will give their informed written consent prior to participation.

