#### HEALTHY CONTROLS: MRI ONLY GROUP

30 healthy controls will undergo an MRI scan, without use of rTMS or TBS. We will offer these 30 healthy controls an optional component involving 2 sessions of 3- 10min of TBS, 1 session on the Magventure TMS device and 1 session on the Nextstim TMS device, in order to compare participant preference between the 2 TMS systems.

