#### EXPERIMENT 1: Heart rate changes

The first experiment will determine what heart rate changes are seen following TMS/TBS stimulation. Please note some participants will only be included in experiment 1, availability and scheduling permitting. Subjects will attend 2 sessions where they will receive TMS/iTBS at 70 -100 of active or resting MT, as determined by the investigator. They will receive either active or sham during a session, and the sessions will be in a randomly assigned order.

Stimulation may be applied to the vertex, Beam F3 location, or location determined by neuronavigation. These are all standard locations for stimulation. Various heart rate measurements and cortisol and/or other lab tests will be collected before and after stimulation. fMRI will be completed before and after stimulation. Various questionnaires (e.g. regarding mood will be collected before/after stimulation). Tasks designed to induce mild mental stress (e.g. mental math or similar) will be used during the experiment to create equivalent baseline conditions for all subjects.

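### Section 5e admits lab personnel without excluding the group running the study, although sections 2a and 5b say every participant is blinded to its purpose

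*Protocol*

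**What the plan says.** On blinding, the Participants part of section 2a says: "They will be recruited to participate in this study, all of whom will be blinded to the purpose of the study". Section 5b repeats the same clause: "all of whom will be blinded to the purpose of the study". Both statements cover everyone recruited.

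On who may enrol, section 5e says: "Employees, students and lab personnel may sign up for this study in compliance HIPAA policy". Section 5c adds: "We will also include employees and students rTMS is a low-risk procedure, but we will ensure all safety measures are taken for these participants". The only condition in 5e concerns privacy law, and the only one in 5c concerns safety.

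On the parts of the study that rely on uninformed participants:

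- Experiment 1 gives each subject two sessions: "They will receive either active or sham during a session, and the sessions will be in a randomly assigned order". Heart rate measures and cortisol or other laboratory tests are taken before and after stimulation, with tasks that induce mild mental stress, and self-report is added: "Various questionnaires (e.g. regarding mood will be collected before/after stimulation".
- Experiment 5 shows film clips chosen to induce affective states during stimulation, and measures brain and motor responses before and after.
- The MRI-only group is offered two optional sessions on different devices, "in order to compare participant preference between the 2 TMS systems".

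**The concern.** Blinding to purpose is stated as a fact about all participants, but the enrolment text expressly admits a category of people who may know the purpose because they work on the study. This is a positive permission in section 5e, so a site that follows the protocol to the letter could enrol its own staff.

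What is at stake is the credibility of comparisons that a participant's expectations can influence. In Experiment 1 each person contributes an active and a sham session. Random session order balances period effects, but an expectation tied to the condition moves with the condition and is not balanced by order. In Experiment 5, someone who knows what a clip is meant to induce is not naive to the induction. In the device comparison the outcome is a stated preference, and someone who works with either device may already hold one.

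**Working it through.** The protocol gives no figure on this point, so the check is a comparison of its sections.

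**1. Is blinding to purpose universal?** Yes. Sections 2a and 5b use the same unqualified wording, and neither makes an exception for staff.

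**2. Does the enrolment text admit people who could know the purpose?** Section 5e names lab personnel and does not say whose laboratory. It therefore does not exclude the conducting group. Employees and students in general, also named in 5c, raise no conflict unless they know the study.

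**3. Does any criterion reconcile the two?**
- The inclusion list in 5h covers age, handedness, agreement to fMRI, suspension of certain medicines, English proficiency and eligibility for payment.
- The exclusion list in 5h covers contraindications to rTMS and MRI, pregnancy or breast feeding, neurological disease, antidepressant use, medication that cannot be stopped, and a motor threshold that cannot be obtained.
- The screening steps in 5i are consent, an enrolment number and an eligibility decision.

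None of these asks about involvement in the study, knowledge of its hypotheses or knowledge of the assignment.

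**4. Consequence.** Take a healthy, right-handed adult member of the conducting group who passes every item in step 3. Section 5e permits enrolment and 5h does not prevent it. That person is likely to know the aims, including the directional hypotheses under Objectives (30 Hz bursts best for cTBS and 50 Hz for iTBS; intervals of 15 and 30 minutes). The statement in 2a and 5b would then be untrue for that person.

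**5. Can the effect be sized?** Suppose k of n participants in a within-person comparison are informed, and knowledge shifts their difference by an average amount d. The mean difference then shifts by (k/n) × d.
- k is not stated.
- d is not stated, and no input for it is given.
- n for Experiment 1 is not stated. The whole MRI+rTMS group is 30, and some participants may join Experiment 1 only.
- The device comparison belongs to the other group of 30 and is optional, so its n is at most 30.

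For scale only, assuming n = 30, one informed person carries 1/30 = 3.3% of the mean; assuming 3 to 6 such people gives 3/30 = 10% to 6/30 = 20%. These shares show how the weight works. They do not estimate a bias.

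**6. Can the direction be given?** Not for the parts at issue. Hypothesis 1 says only that heart rate will change, Hypothesis 6 only that responses will differ by affective state, and the device comparison has no stated hypothesis. The directional hypotheses in step 4 belong to Experiments 2 and 3, which rest on motor evoked potentials and have no sham session.

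**The case against.** The strongest reply is that the texts can be read together: personnel may volunteer, but whoever is enrolled must be blinded to purpose, so study staff are excluded by implication. Lab personnel may also mean people from other Stanford laboratories. Both readings are possible, and they make this a conflict the text fails to prevent, not proof that insiders will be enrolled. They do not remove the point. Eligibility is decided against the lists in 5h, and nobody applying them is told to ask what a volunteer knows.

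Several stronger readings are tempting and are not supported:

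- *That the whole study is sham-controlled and rests on questionnaires.* Only Experiment 1 describes a sham session. Most measures are physiological or imaging measures, and the primary endpoint in section 2g is the duration of the effect of TBS.
- *That informed participants would push results in the expected direction.* The hypotheses relevant to the exposed comparisons state no direction.
- *That admitting staff breaks a promise about sham.* Sections 2a and 5b promise blinding to purpose, which is different from blinding to allocation. Recognising sham would not contradict them. Nor is that risk confined to staff, since each Experiment 1 subject receives both conditions and some may also have active stimulation in other experiments.
- *That the critical feedback task adds to the case.* That task "provides them with accurate or bogus feedback on their performance", while section 2c says that no deception is used. Whether participants are meant to be unaware of the false feedback is therefore unclear. That is a separate question and is not relied on here.

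**Conclusion.** The point holds as a conflict between sections 5e and 2a/5b that the criteria in 5h leave open. It rests on two readings of the text: that lab personnel is not limited to other laboratories, and that a member of the conducting group would know the study's purpose. The second is a reasonable inference, not a stated fact.

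Its reach is limited to the parts that expectation can plausibly affect: Experiment 1's active/sham comparison, Experiment 5's affect induction and the stated device preference. Size and direction cannot be computed from the protocol, and the shares shown above are assumptions. It is worth correcting because section 5e grants the permission expressly and the remedy is small.

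**What to change.** Add one exclusion criterion to section 5h: members of the research group conducting this study, and anyone who knows its hypotheses or the active/sham assignment. Amend section 5e so that other employees, students and lab personnel may enrol only if they meet that criterion. The statements in 2a and 5b can then stand as written. If the investigators wish to keep their own staff eligible, the alternative is to withdraw the claim that all participants are blinded to purpose.

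The cost is one line in 5h, a wording change in 5e and the loss of a few convenient volunteers. The research registry described in section 5g, with over 1,000 volunteers, remains available.

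This change secures blinding to purpose. It does not by itself ensure that participants cannot tell sham from active. Recording prior TMS experience, and asking each Experiment 1 participant after each session which condition they think they received, would allow that to be checked separately.

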### f. Healthy Volunteers

All participants are healthy volunteers.

### g. Recruitment Details

We intend to recruit 30 healthy subjects. We will obtain IRB approval for flyers advertising the study.

We will be utilizing social media to reach potential participants. We have a Facebook page for our research group that we will use to promote the study. We will do so using only IRB approved language.

We will also begin utilizing the Stanford Research Registry (protocol 25422) to recruit study participants. The research registry is a list of individuals who have consented to be contacted by research at Stanford and at present includes over 1,000 volunteers.

---

#### **h. Eligibility Criteria**

##### **i. Inclusion Criteria**

1. Age 18-80 years old
2. Right-handed
3. Agree to having fMRI scan
4. Willingness to suspend use of analgesic drugs or cough suppressants for 24 hours prior to the scans
5. Proficiency in English sufficient to complete questionnaires/follow instructions during fMRI assessments
6. US Citizen or resident able to receive payment legally

##### **ii. Exclusion Criteria**

1. A medical condition that would contraindicate the use of rTMS
2. Any condition that would contraindicate MRI (like ferromagnetic metal in the body)
3. Pregnancy or breast feeding
4. Any significant neurologic disease, including dementia, multi-infarct dementia, Parkinson's or Huntington's disease, brain tumor, progressive supranuclear palsy, seizure disorder, subdural hematoma, multiple sclerosis, history of significant head trauma.
5. Current antidepressant use (must be washed out for two weeks prior to starting protocol).
6. Inability to stop taking medication contraindicated with treatment.
7. Motor threshold is unable to attained.

---

